### 2.3.2 KNOWN POTENTIAL BENEFITS

**For participants randomized to receive a sham treatment:** There will be no difference between being in this study and deciding against participation. Therefore, there is no potential for direct benefits from this sham “treatment”.

**For participants randomized to receive active cryoneurolysis:** It is our hope that patients have a decrease in phantom and/or residual limb pain which might decrease supplemental analgesic consumption, analgesic-related side effects (e.g., opioid-related sedation), and interference of pain in physical and emotional functioning.

**Possible benefits to others:** Future patients may benefit if it is determined that cryoneurolysis decreases pain following trans-femoral amputation. In addition, with the opioid epidemic, any decrease in opioid requirements would be a welcome development.

---

### 2.3.3 ASSESSMENT OF POTENTIAL RISKS AND BENEFITS

Chronic phantom pain causes significant disability for patients, and there is currently a dearth of reliable treatments for this debilitating pain. Even chronic pain described as “mild” has a significant negative impact on physical and mental health, as well as substantially decreasing overall quality of life.

In contrast, the risks of cryoneurolysis are minimal compared with the common treatment of a peripheral nerve block. There have no previous cases of permanent negative sequelae reported in the literature, and we therefore believe that the potential risks of cryoneurolysis are minimal compared to the potential benefits.

### 3 OBJECTIVES AND ENDPOINTS

OBJECTIVES	ENDPOINTS	JUSTIFICATION FOR ENDPOINTS
Primary		
To estimate the analgesic effect of cryoneurolysis on intractable post-amputation (trans-femoral) phantom limb pain 1 month post-treatment	Phantom limb pain intensity will be significantly decreased relative to baseline pain 1 month following a cryoneurolysis procedure (as measured by the Numeric Rating Scale within the Brief Pain Inventory).	Pain negatively influences physical and emotional functioning.
Secondary		
To estimate the analgesic effect of cryoneurolysis on intractable post-amputation (trans-femoral) phantom limb pain at various time points post-treatment (Days 1, 7, and Months 2, 3, 4, and 12)	Phantom limb pain intensity will be significantly decreased relative to baseline pain at various time points following a cryoneurolysis procedure (as measured by the Numeric Rating Scale within the Brief Pain Inventory).	Pain negatively influences physical and emotional functioning.
To estimate the analgesic effect of cryoneurolysis on intractable post-amputation (trans-femoral) residual limb pain at various time points post-treatment (Days 1, 7, and Months 1, 2, 3, 4, and 12)	Residual limb pain intensity will be significantly decreased relative to baseline pain at various time points following a cryoneurolysis procedure (as measured by the Numeric Rating Scale within the Brief Pain Inventory).	Pain negatively influences physical and emotional functioning.
To estimate the effect of cryoneurolysis on the perception of well-being in patients with intractable post-amputation (trans-femoral) phantom limb pain	The perception of well-being as measured with the Patient Global Impression of Change Scale will be improved at various time points following a cryoneurolysis procedure (Days 1, 7, and Months 1, 2, 3, 4, and 12)	Global perception of well-being is indicative of patients' own perception of their life status.
To estimate the effect of cryoneurolysis on the physical and emotional functioning of patients with intractable post-amputation (trans-femoral) phantom limb pain	The physical and emotional functioning of patients will be improved at various time points following a cryoneurolysis procedure relative to baseline as measured with the Brief Pain Inventory Interference Subscale(Days 1, 7, and Months 1, 2, 3, 4, and 12)	Pain negatively influences physical and emotional functioning.
Tertiary/Exploratory		

OBJECTIVES	ENDPOINTS	JUSTIFICATION FOR ENDPOINTS
To estimate the effect of cryoneurolysis on the incidence and duration of non-painful phantom sensations in patients with intractable post-amputation (trans-femoral) phantom limb pain	The incidence and duration of non-painful phantom sensations will be improved at various time points following a cryoneurolysis procedure (Days 1, 7, and Months 1, 2, 3, 4, and 12)	Even non-painful phantom sensations may negatively influence patient well-being.
To estimate the effect of cryoneurolysis on the incidence and duration of phantom limb pain in patients with intractable post-amputation (trans-femoral) pain	The incidence and duration of phantom limb pain will be improved at various time points following a cryoneurolysis procedure (Days 1, 7, and Months 1, 2, 3, 4, and 12)	Pain negatively influences physical and emotional functioning.
To estimate the effect of cryoneurolysis on the incidence and duration of residual limb pain in patients with intractable post-amputation (trans-femoral) pain	The incidence and duration of residual limb pain will be improved at various time points following a cryoneurolysis procedure (Days 1, 7, and Months 1, 2, 3, 4, and 12)	Pain negatively influences physical and emotional functioning.

## 4 STUDY DESIGN

### 4.1 OVERALL DESIGN

The study is a single-center, randomized, participant- and observer-masked, active-controlled, parallel-arm, optional crossover, human-subjects, post-market clinical pilot study to investigate the use of ultrasound-guided percutaneous cryoneurolysis to treat phantom limb pain following a trans-femoral (above-knee) amputation. Participants with intractable phantom limb pain will be randomly allocated to one of two possible treatment groups: cryoneurolysis (experimental) or sham (control). The primary outcome measure is the change in the phantom limb pain intensity from baseline 1 month following the procedure as measured by the Numeric Rating Scale within the Brief Pain Inventory.

### 4.2 SCIENTIFIC RATIONALE FOR STUDY DESIGN

Over 200,000 traumatic and surgical amputations occur annually within the United States alone; with an estimated 1.6-million people living with an amputation, and this number is expected to double by 2050. Among amputees, 35-98% (depending on the study) develop chronic, intractable pain perceived as being from the missing limb, a phenomenon termed “phantom limb pain”. The pain is usually described as “shooting, stabbing, boring, squeezing, throbbing, and burning”. Unfortunately, phantom pain resolves in only 16% of afflicted individuals (with or without treatment). The rest will experience phantom pain for the remainder of their lives, with most becoming dependent upon chronic opioid use to gain even a small degree of relief. There is currently no reliable, definitive treatment for phantom limb pain.

[figure not shown]

The exact reason that phantom limb pain occurs is unclear, but when a nerve is cut—as happens with an amputation—changes occur in the brain and spinal cord that increase with worsening phantom pain. These abnormal changes may often be corrected by putting local anesthetic—called a “nerve block”—on the injured nerve, effectively keeping any “bad signals” from reaching the brain with a simultaneous resolution of the phantom limb pain. However, when the nerve block resolves after a few hours, the phantom pain returns. But this demonstrates that the brain abnormalities—and phantom pain—that occur with an amputation are not necessarily fixed and may be dependent upon the “bad” signals being sent from the injured nerve(s). This, in turn, suggests that a very long peripheral nerve block—lasting many months rather than hours—may permanently reverse the abnormal changes in the brain and provide definitive relief from phantom pain. A prolonged nerve block lasting a few months may be provided by freezing the nerve using a process called “**cryoneurolysis**”. **The ultimate objective of the proposed research study is to determine if cryoanalgesia is an effective treatment for intractable post-amputation phantom limb pain.**

**An alternative analgesic technique is cryoneurolysis,** consisting of the application of exceptionally low temperatures to reversibly ablate peripheral nerves, resulting in temporary pain relief termed “cryoanalgesia”.

The intense cold temperature at the probe tip produces Wallerian degeneration—a reversible breakdown of the nerve axon—subsequently inhibiting transmission of afferent and efferent signals. Because the nerve endoneurium, perineurium, and epineurium remain intact, the axon regenerates along the exoskeleton at a rate of approximately 1-2 mm/day. While cryoneurolysis of peripheral nerves through surgical incisions has been commonly used to treat pain since 1961, the

development of cryo probes that may be inserted percutaneously promise a revolution in the use of this modality. The combination of newly-designed cryoneurolysis devices (above right), the narrow-gauge probes (immediate right), and ultrasound now make percutaneous cryoanalgesia as simple as placing a peripheral nerve block: the probe tip is inserted adjacent to the target nerve under ultrasound guidance, the probe tip is frozen and subsequently withdrawn. **The procedure is essentially the same as placing an ultrasound-guided peripheral nerve block; however, instead of injecting local anesthetic, a gas circulates through the probe, inducing cold at the tip and freezing the target nerve.** Nothing remains within the patient and there is no external equipment to prepare or manage. Importantly, cryoneurolysis and the cryo probes are already approved by the United States Food and Drug Administration for the treatment of pain, including phantom limb pain, so no additional regulatory approval is required for the proposed clinical trial.

Theoretical benefits of cryoneurolysis include an ultra-long duration of action without opioid involvement, no catheter management/removal, the lack of an infusion pump and anesthetic reservoir to carry, an extraordinarily low risk of infection (approaching zero), and no risk of local anesthetic toxicity, catheter dislodgement or leakage. With a single percutaneous cryoneurolysis procedure, nerve conduction is attenuated 2-3 months with the complete restoration of nerve structure and function following remyelination.

**There is currently no reliable treatment for phantom limb pain.** While more than 43 methods for treating phantom pain have been described, the placebo effect is common, and prolonged relief is experienced by fewer than 10% of treated patients (6% of untreated patients ultimately experience spontaneous resolution). Evidence of the intractable nature of phantom pain may be found in a survey of more than 10,000 amputees which reported a 1% treatment success rate. **Therefore, the overwhelming majority of people suffering from phantom limb pain are dependent upon opioid analgesics to gain even a small degree of relief.** There are few data from randomized trials to guide treatment, leading the authors of a major review to conclude that there remains a substantial “gap between research and practice in the area of phantom limb pain”.

We have completed and published a Department of Defense-funded multicenter, randomized, double-masked, sham-controlled clinical trial investigating the use of ultrasound-guided percutaneous cryoneurolysis to treat existing post-amputation phantom limb pain (UCSD IRB 170973, now closed). In short, patients who had a below-the-knee amputation (BKA) experienced prolonged benefit from active treatment ( $P=0.003$ ); but patients who had an above-the-knee amputation (AKA) did not experience similar analgesia. Therefore, because the study was designed to analyze these two amputation levels together, the overall findings were negative ( $P=0.759$ ). There is subsequently published evidence that the nitrous-oxide-based equipment that was used (PainBlocker, Epimed International, Dallas, TX) did not form a large or cold enough ice ball to adequately treat the larger nerves of the upper thigh for AKAs, resulting in a neuropraxia that worsened pain. We theorize that the nitrous-oxide-based equipment that was used (PainBlocker, Epimed International, Dallas, TX) did not form a large or cold enough ice ball to adequately treat the larger nerves of the upper thigh for AKAs. In contrast, the ice ball size/temperature was adequate to treat the smaller nerves of the lower thigh for BKAs, resulting in cryoneurolysis and prolonged analgesia.

Given chronic pain’s enormous costs to individuals and society—and the intractable, currently-untreatable nature of phantom limb pain with concurrent opioid dependence—it is imperative that an effective treatment be developed. If our study demonstrates that ultrasound-guided percutaneous cryoneurolysis is a successful treatment, the resulting impact on the hundreds-of-thousands of Americans suffering from intractable phantom limb pain will be **immediate and profound**, as (1) healthcare providers within the United States Armed Forces, Veterans Affairs Medical Centers, and civilian hospitals already have expertise placing ultrasound-guided peripheral nerve blocks; (2) cryoneurolysis is a relatively inexpensive, single-procedure, outpatient treatment with few complications; and (3) cryoanalgesia is already approved by the United States Food and Drug Administration.

### 4.3 JUSTIFICATION FOR DOSE

Not Applicable for this protocol which does not investigate a medication.

### 4.4 END OF STUDY DEFINITION

The end of the study is defined as completion of the last follow up data collection time point (12 months) of the final enrolled participant.

## 5 STUDY POPULATION

A total of 20 individuals are anticipated for the analysis. However, to account for dropouts, will be requesting an additional 5 participants. This will total up to 25 participants.

### 5.1 INCLUSION CRITERIA

- (1) Adult patients of at least 18 years of age
- (2) Trans-femoral traumatic or surgical amputation at least 12 weeks prior to enrollment distal to the hip (femoral head remaining)
- (3) Experiencing at least moderate phantom limb pain—defined as a 4 or higher on the Numeric Rating Scale (NRS; 0-10, 0= no pain; 10=worst imaginable pain)—at least daily for the previous 2 months
- (4) Willing to avoid both changes to their analgesic regimen as well as elective surgical procedures from 1 month prior to and at least 4 months following the initial cryoneurolysis procedure

### 5.2 EXCLUSION CRITERIA

- (1) allergy to amide local anesthetics
- (2) pregnancy
- (3) incarceration
- (4) inability to communicate with the investigators
- (5) morbid obesity (body mass index > 40 kg/m^2)
- (6) possessing any contraindication specific to cryoneurolysis such as a localized infection at the treatment site, cryoglobulinemia, cold urticaria and Reynaud's syndrome

### 5.3 LIFESTYLE CONSIDERATIONS

NOT APPLICABLE.

## 5.4 SCREEN FAILURES

Screen failures are defined as participants who consent to participate in the clinical trial but are not subsequently randomly assigned to the study intervention or entered in the study.

# 6 STUDY INTERVENTION

## 6.1 STUDY INTERVENTION(S) ADMINISTRATION

### 6.1.1 STUDY INTERVENTION DESCRIPTION

For individuals of childbearing potential, a sample of urine will be collected before any study interventions to confirm a non-pregnant state.

**Treatment group allocation (randomization).** Participants will be allocated to one of two possible treatments groups:

1. *Cryoneurolysis*
2. *Sham procedure (Control)*

Randomization lists will be created using computer-generated tables by the Investigational Pharmacy (UC San Diego) in a 1:1 ratio and block sizes of 2. Treatment group assignment will be conveyed to the investigators in the form of sealed, opaque envelopes only by the treating investigator. Therefore, all investigators and participants will be masked to treatment group assignment, with the only exception being the investigator who performs the procedure (and will not have subsequent contact with the participant). ***This protocol will enable a randomized, observer- and participant-masked, sham/placebo-controlled study.*** It is impossible to mask the individual performing the cryoneurolysis procedure because the ice ball forming at the distal end of the probe—with *active* treatment—is clearly visible by ultrasound; and the lack of an ice ball for placebo participants is equally clear. It is essential to continuously visualize the probe and target nerve throughout the two freeze/thaw cycles to ensure the entire nerve diameter is adequately treated and remains relatively motionless. This cannot be achieved if the ultrasound is turned off during nitrous oxide administration to mask the provider; and we prioritize patient safety over masking of the physician administering the intervention. All participants will have a peripheral intravenous (IV) catheter inserted, standard noninvasive monitors applied (blood pressure cuff, pulse oximeter, 5-lead ECG), and oxygen administered *via* a nasal cannula or facemask. Midazolam and fentanyl (IV) will be titrated for patient comfort, while ensuring that patients remain responsive to verbal cues.

The cryoneurolysis sites will be cleansed with chlorhexidine gluconate and isopropyl alcohol. ***The nerves treated will include the femoral, sciatic, obturator, and lateral femoral cutaneous.*** Each nerve will be visualized using ultrasound, a skin wheal of local anesthetic will be raised inferior to the transducer to anesthetize the skin and then the track towards the target nerve. The probe will then be inserted adjacent to the target nerve. The cryoneurolysis machine (CryoCare, Varian Medical Systems, Palo Alto, California) uses argon for the freeze cycle and helium to help decrease the thaw period duration. The cryoneurolysis device will be triggered using 1 cycle of 5.5-minute argon activation (2000-2500 PSI and 100% power) followed by a 30-second helium defrost. The Varian machine provides its own timer so that the gas cycle timing is precise to the second. This may be repeated, as necessary, to ensure the entire cross-section of each nerve is fully treated.

**Active Cryoneurolysis.** For participants randomized to active treatment, the probe placed in the patient will be triggered and the argon (and helium) passed through the probe and then back into the machine, and finally vented out from the console. This will result in a freeze-thaw cycle.

**Control.** For participants randomized to sham treatment, the probe in the patient will simply not be activated; instead, a second probe that is not inserted in the patient will be triggered which will create the same visual and auditory cues as for the active participants retaining the masked feature. The investigator administering the study intervention will activate the correct probe depending on the treatment group assignment. Therefore, all investigators and participants will be masked to treatment group assignment, with the only exception being the unmasked investigator who performs the procedure (and will not have subsequent contact with the participant).

It is impossible to mask the individual performing the cryoneurolysis procedure because the ice ball forming at the distal end of the probe—with active treatment—is clearly visible by ultrasound; and the lack of an ice ball for sham participants is equally clear. It is essential to continuously visualize the probe and target nerve throughout the freeze/thaw cycle(s) to ensure the entire nerve diameter is adequately treated and remains relatively motionless. This cannot be achieved if the ultrasound is turned off during nitrous oxide or argon administration to mask the provider; and we prioritize patient safety over masking of the physician administering the intervention.

Prior to discharge, subjects will be provided with verbal and written instructions, the telephone and pager numbers of an investigator, and a copy of the Institutional Review Board-approved consent form. The approximate duration of this visit will total 4 hours, from the time the subject enters the treatment facility until the time the depart.

**Optional crossover treatment.** Four to six months following the initial treatment, subjects *may* return for an optional repeated intervention procedure (“crossover”) with the alternative treatment (either active cryoneurolysis or sham/placebo), again in a double-masked fashion using the same protocol as described for the initial intervention. **The crossover treatment is not required for study participation, as the primary analyses will include a parallel study design for the initial intervention evaluated prior to any crossover treatment.** However, an optional crossover treatment will be offered to subjects for two reasons: (1) it will ensure that all subjects have access to the proposed treatment, regardless of the treatment they are initially randomized to; and (2) it will permit intra-subject differences between treatments to be analyzed (e.g., assessing treatment-effect heterogeneity, or the variability of the causal effect across individuals, which will would not be available from the parallel-group portion of the study alone). These intra-subject differences will be secondary analyses, as there may be patient-selection bias regarding which subjects decide to have the crossover treatment (e.g., if the intervention is successful at greatly reducing phantom limb pain, then subjects receiving active cryoneurolysis during their initial treatment will be more likely to forgo the crossover treatment). This crossover will *not* affect the primary analyses, which will involve a parallel group study design and investigate the effects of cryoneurolysis within 4 months of the initial intervention. The approximate duration of a crossover visit will total 4 hours, from the time the subject enters the treatment facility until the time the depart. Following study completion, the results will be provided to all enrolled subjects using non-technical (i.e. “layperson”) language, along with their treatment group assignment at the participants’ request.

Following study completion, the results will be mailed electronically or by the United States Postal Service to all enrolled participants in written form using non-technical (e.g., “layperson”) language.

---

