1 PROTOCOL SUMMARY	
1.1 SYNOPSIS	
Title:	Cryoanalgesia to Treat Phantom Limb Pain following a Trans-Femoral (Above-Knee) Amputation: A Randomized, Sham-Controlled Pilot Study
Study Description:	
The study is a single-center, randomized, participant- and observer-masked, active-controlled, parallel-arm (optional crossover), human-subjects, post-market clinical pilot study to investigate the use of ultrasound-guided percutaneous cryoneurolysis to treat phantom limb pain following a trans-femoral (above-knee) amputation. A prolonged nerve block may be provided by freezing the nerve using a technique called “cryoneurolysis”. With cryoneurolysis and ultrasound machines, a small needle-like “probe” may be placed through anesthetized skin and guided to the target nerve to allow freezing. The procedure takes about 6 minutes for each nerve, involves little discomfort, has no systemic side effects, and cannot be misused or become addictive. After 2-3 months, the nerve returns to normal functioning. Participants will be randomly allocated to one of two possible treatments groups: cryoneurolysis (experimental) or sham (control). The primary outcome measure is the change in the phantom limb pain intensity from baseline 1 month following the procedure as measured by the Numeric Rating Scale within the Brief Pain Inventory.

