## 8.2 SAFETY AND OTHER ASSESSMENTS

Prospective subjects will be provided with informed consent and then screened for inclusion and exclusion criteria. The following safety and eligibility procedures will occur during that time:

- **Study Eligibility** – A study investigator will review all medical history, medications and the inclusion/exclusion criteria with the participants.
- **Informed Consent** - Participants will provide written informed consent prior to any other study procedures.
- **Vital Signs** – These include blood pressure, heart rate, temperature and respiratory rate as well as pulse oximetry and continuous 5-lead ECG.
- **Adverse Event Collection** – Patients’ progress notes will be followed during hospitalization and any adverse events recorded. Following discharge, investigators will inquire about any adverse or unexpected events that have occurred since the previous contact. All events will be evaluated by a study investigator and will be followed until resolution.

Any of the safety assessment results will be made available to participants should they request them.

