### **10.1.8.1 DATA COLLECTION AND MANAGEMENT RESPONSIBILITIES**

The investigators will create a hard-copy case report form for each study participant enrolled, which will include only the randomization number and first/last name initials (as a check), anthropometric (e.g., age, height, weight), and demographic information. All case report forms will be identified by only the randomization number and first and last initial of the participants' names (as a check for the randomization numbers). Therefore, any protected health information will be separated from identifiers. The connection between participant identifiers and the randomization numbers will be accessible solely by the Principal Investigator and Program Manager (for follow-up data collection purposes). Therefore, no case report form will be tied to an identifiable individual on the forms themselves, ensuring patient confidentiality should a form be inappropriately accessed. All enrollment and case report forms will be retained in the locked offices of the Principal Investigator and/or Program Manager. The data from each enrollment form will be uploaded to the project database. These hard copies will not be mailed or otherwise transferred and will remain available to audit for a minimum of 7 years.

---

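### Fixed blocks of 2 let an operator who knows the first assignment of a pair foresee the second, and the plan does not keep the operator out of enrolment decisions

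*Combined protocol and SAP*

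**What the plan says.** Section 6.1.1 gives the Investigational Pharmacy the task of generating the list "in a 1:1 ratio and block sizes of 2". It names no other block size, no random variation and no stratification factor. The Synopsis (1.1) describes the design: "The study is a single-center, randomized, participant- and observer-masked".

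Assignments are conveyed "in the form of sealed, opaque envelopes only by the treating investigator". The operator is the declared exception to masking: "all investigators and participants will be masked to treatment group assignment, with the only exception being the investigator who performs the procedure". The reason given is physical: "It is impossible to mask the individual performing the cryoneurolysis procedure because the ice ball forming at the distal end of the probe" shows on ultrasound. The operator must also choose which probe to activate. So the operator knows the assignment of every participant he or she treats.

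Eligibility is covered in 8.2: "A study investigator will review all medical history, medications and the inclusion/exclusion criteria with the participants". Section 10.1.1 has an investigator or research coordinator screen candidates by telephone, after which those who qualify are scheduled. Neither section says whether the operator may fill these roles.

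Section 10.1.8.1 states: "All case report forms will be identified by only the randomization number and first and last initial of the participants' names". Section 10.1.3 says the same. Section 6.3 allows the Principal Investigator to be unmasked after the primary outcome measure.

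**The concern.** Sealed envelopes conceal an assignment only from someone who cannot deduce it. The block size is printed in the protocol, so an operator who has just treated the first member of a pair can deduce the second member's arm without opening anything.

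That knowledge matters if the same person can influence who comes next or when. The Schedule of Activities (1.3) puts consent, screening, randomization and treatment all on Day 0. Section 9.4.5 analyzes participants who received any study treatment, so a candidate deferred or turned away beforehand never enters the analysis. Section 10.1.1 records reasons for exclusion without identifiers, and 10.1.7 provides no formal monitoring, so selective deferral would be hard to see afterwards.

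At stake is the between-group difference at month 1. The Synopsis says the study is to estimate the treatment effect to help size a definitive trial. An estimate distorted by selection would carry into that design and could not be repaired in analysis.

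**Working it through.** The plan states no figure for predictability, so there is none to reproduce. The check enumerates what the stated rule implies.

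**Inputs.** Ratio 1:1 and block size 2 (6.1.1). Single center, no stratification stated, so one sequence is assumed (1.1, 6.1.1). Analysis target 20 (9.2); enrolment up to 25 (5, 9.3). The person predicting knows all earlier assignments.

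**Certain assignments.** The only possible blocks are active–sham and sham–active. The first member has probability 1/2; the second, given the first, has probability 1.

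- N = 20: 20/2 = 10 complete pairs, so 10/20 = 50% are certain in advance.
- N = 25: 12 complete pairs and one unpaired participant, so 12/25 = 48%.

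**Best guess.** First members are guessed correctly half the time, second members always.

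- N = 20: 10 × 0.5 + 10 × 1 = 15, and 15/20 = 75%.
- N = 25: 13 × 0.5 + 12 × 1 = 18.5, and 18.5/25 = 74%.

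Simple randomization would give 50%.

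**Pair-mate inference.** Suppose randomization numbers follow list order (an assumption), so that pairs are 1–2, 3–4 and so on. If k of 20 participants are unmasked at random, the expected number of known assignments is 20 × [1 − C(18,k)/C(20,k)].

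- k = 1: 20 × (1 − 18/20) = 2.0
- k = 2: 20 × (1 − 153/190) = 3.9
- k = 3: 20 × (1 − 816/1140) = 5.7
- k = 5: 20 × (1 − 8568/15504) = 8.9

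**Alternatives at N = 20.** For one block of size 2m, the expected share guessed correctly is [m + (4^m/C(2m,m) − 1)/2]/(2m). For a list of 20, m = 10: 4^10/C(20,10) = 1048576/184756 = 5.675, so [10 + 4.675/2]/20 = 61.7%. Certain shares come from enumeration. The mixed-block row comes from 20,000 simulated lists, with a guesser who knows the two possible sizes but not their order.

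| Scheme | Certain in advance | Guessed correctly |
|---|---|---|
| Fixed 2 (plan) | 50.0% | 75.0% |
| Fixed 4 | 33.3% | 70.8% |
| Fixed 6 | 22.5% | 67.0% |
| Random 4 or 6 | about 5.8% | about 68.5% |
| One permuted list of 20 | 9.1% | 61.7% |

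For fixed blocks of 6, 20 participants make three complete blocks with 1.5 certain positions each, plus two positions that are never certain: 4.5/20 = 22.5%.

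**Cost in balance.** With equal standard deviations, the variance of a difference in means is proportional to 1/n1 + 1/n2, which is 0.2 for 10:10.

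- 11:9: (1/11 + 1/9)/0.2 = 1.01, a 1% increase.
- 12:8: (1/12 + 1/8)/0.2 = 1.04, a 4% increase.

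**The case against.** The arithmetic is not in dispute; what follows from it is.

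**Foreknowledge is conditional.** It requires one operator, or several who share results; envelopes used in list order; and the first member of a pair treated before the second is screened or booked. The plan does not give the number of operators. Section 6.1.1 says the operator will not see the participant again, which read literally would call for a second operator at any crossover. Section 10.1.1 has candidates screened by telephone and then scheduled, so a pair-mate could already be booked. These points stand and are written into the verdict as assumptions.

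**Discretion is limited.** Most criteria in 5.1 and 5.2 are factual (age, amputation level, pain score, body mass index, pregnancy), and coordinators may screen and obtain consent. This narrows the route but leaves open timing, scheduling and the decision to proceed.

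**A reader might infer that allocation concealment fails for half the trial.** The documents do not support that. A determined assignment does harm only if someone who knows it influences enrolment, and the plan is silent on the operator's role there. Silence is a gap to close, not evidence of failure.

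**A reader might also infer that assessor masking fails in pairs.** That goes too far. An assessor would first have to learn one assignment, and the numbers would have to follow list order. Section 8.1 has masked staff collect outcomes by telephone after Day 0, so they would not observe a sensory or motor block. Unmasking under 6.3 is for the Principal Investigator alone. What remains is narrower. Section 10.1.3 gives the Principal Investigator the link between identity and number, and 6.3 does not say whether unmasking waits for every participant's month-1 assessment. If it does not, a pair-mate not yet treated, or not yet at month 1, could become known.

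**It is a pilot.** Section 9.4.9 calls all analyses exploratory. That lowers the urgency, but estimating the effect is a stated purpose and 9.1 sets a significance threshold for the primary outcome.

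**Conclusion.** The point holds as an avoidable design weakness that should be fixed. With fixed blocks of 2, 10 of 20 assignments (12 of 25 at full enrolment) are certain once the preceding one is known, and the best guess is right 75% (74%) of the time. This rests on one operator or shared results, envelopes used in order, and first members treated before their pair-mates' enrolment is settled. Envelopes, masked assessors and the bar on later operator contact do not hide the next assignment from that operator.

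The consequence is an opportunity for selection bias. Nothing in the documents shows that it would be taken or how far it would move the estimate. Pair-wise unmasking is a secondary risk that depends on list-order numbering and on someone first learning an assignment.

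**What to change.** For the remaining envelopes, preferably starting after a completed pair:

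1. Have the Investigational Pharmacy generate randomly varying blocks of 4 and 6, or one permuted list, and hold the block details outside the protocol. The figures above are for a fresh list of 20; those for a shorter remainder will differ.
2. State in 6.1.1, 8.2 and 10.1.1 that the operator takes no part in eligibility, enrolment or scheduling decisions. This is the most direct control and works under any block scheme.
3. Optionally, identify case report forms by a study ID that does not follow the randomization sequence.

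Changing when envelopes are opened would not help, because a determined assignment is known without opening one.

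The cost is a new pharmacy list and a minor amendment, extended to 10.1.3 and 10.1.8.1 if the ID changes. The statistical cost is a possible small imbalance: 1% more variance at 11:9, 4% at 12:8. Pairs already allocated cannot be re-concealed.
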